4.6.3.4 Readmission Within 30 Days of Discharge

The proportion of patients readmitted to the hospital within 30 days of discharge will be summarized by treatment group and analyzed using logistic regression. The model will be adjusted as specified in Section 4.6. Observed counts and percentages for tenecteplase and placebo arms, and model based odds ratio, corresponding Wald 95% CI and p-value will be produced.

4.6.3.5 Patients Requiring One Pass with Endovascular Therapy Device

This endpoint will be defined for endovascular patients for whom the mechanical thrombectomy was performed (i.e. the clot was able to be reached) and a final TICI of 2b or 3 was achieved at the completion of the procedure. The number of passes to reach final TICI 2b/3 will be categorized as 1 vs >1, and analyzed using logistic regression, adjusting as specified in Section 4.6 but excluding the planned thrombectomy variable. If multiple mechanical thrombectomies were reported for a subject, only the initial procedure will be used to define this endpoint. Observed counts and percentages for tenecteplase and placebo arms, and model based odds ratio, corresponding Wald 95% CI and p-value will be produced.

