4.2 METHOD OF TREATMENT ASSIGNMENT AND BLINDING

4.2.1 Treatment Assignment

Site personnel may screen all potential patients in the interactive web response systems (IWRS) in order to assign two study kit numbers (i.e., 1 placebo and 1 tenecteplase) to start the investigational medicinal product (IMP) preparation.

Once the patient meets all eligibility criteria (see Section 4.1.1 and Section 4.1.2) and the consent is signed, site personnel will randomize the patient in IWRS and the system will inform which of the two assigned study kits will be administered. The other study kit will be destroyed or returned to Sponsor. Documentation of secondary

review/verification of study kit administered and discarded should be collected for all dosed patients.

Patients will be randomized 1:1 to receive a single bolus injection of tenecteplase or placebo over 5 seconds. *Patients should* be treated as soon as possible after randomization. Patients are considered enrolled in the study once they have been randomized.

Patients not eligible after screening in IWRS will be recorded as screen failures and both study kits will be destroyed or returned to Sponsor.

Randomization will be stratified by age (≤ 70 vs. > 70 years of age), type of occlusion (ICA/M1 vs. M2), baseline NIHSS (≤ 15 vs. > 15), and randomization site (ECC vs. nECC). Permuted block randomization will be used to achieve the balance of treatment arm assignments within each randomization stratum.

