2.2.3 Exploratory Efficacy Endpoints

The following exploratory efficacy endpoints will be analyzed:

- Median final infarct volumes at 72-96 hours visit or discharge (if patient is being discharged prior to 72-96 hours visit).
- Median infarct growth at 72-96 hours visit or discharge (if patient is being discharged prior to 72-96 hours visit).
- Ordinal mRS score at Day 90 by occlusion type (M1/ICA or M2 occlusions).
- Ordinal mRS score at Day 30 and Day 90 by randomization site (ECC or nECC).
- Proportion of patients who are randomized at an nECC and transferred to an ECC for endovascular therapy for whom planned thrombectomy was not performed.
- Proportion of patients readmitted within 30 days from discharge.
- Proportion of patients requiring one pass with endovascular therapy device (endovascular patients only).
- Mean Quality of Life in Neurological Disorders (Neuro-QoL) scores by domain.
- Proportion of patients where planned thrombectomy was not performed.
- Overall survival at Day 90.

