4.1 ANALYSIS POPULATIONS

4.1.1 Efficacy Analysis Population

All efficacy analyses will be based on the intent-to-treat (ITT) population, defined as all randomized patients who provided informed consent, and analyzed according to the treatment assignment at randomization.

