4.6.2.4 Angiographic Reperfusion

Angiography is a tool that can measure reperfusion, or restoring the flow of blood, after a stroke or heart attack. The Thrombolysis in Cerebral Infarction (TICI) scale is a grading system that is commonly used to measure the response of thrombolytic therapy in ischemic strokes, using angiographic reperfusion (Higashida RT et al, 2003). TICI scores range from grade of 0 (no reperfusion) to grade 3 (complete reperfusion). Grade 2 (partial reperfusion) is further subdivided into 2a and 2b.

In this study, a secondary efficacy endpoint is the proportion of patients with angiographic reperfusion, defined as achieving TICI 2b or TICI 3 at completion of the angiographic procedure. This analysis will be limited to endovascular patients only. Logistic regression will be used to determine the odds of having an angiographic reperfusion, adjusted as specified in Section 4.6. Observed counts and percentages for tenecteplase and placebo arms, and model based odds ratio, corresponding Wald 95% CI and p-value will be produced.

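### The exploratory one-pass endpoint is computed only among thrombectomies that ended in TICI 2b/3, so failures leave the denominator and the comparison between arms can be distorted

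*SAP*

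**What the plan says.** The endpoint lists in Protocol Section 2 (Table 3) and SAP 2.2.3 give the same definition. SAP 2.2.3 reads: "Proportion of patients requiring one pass with endovascular therapy device (endovascular patients only". The only restriction there is to endovascular patients; neither list mentions a TICI grade.

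SAP 4.6.3.5 sets two conditions for entering the analysis. Thrombectomy must have been performed, in the sense that the clot could be reached, "and a final TICI of 2b or 3 was achieved at the completion of the procedure". The outcome is then coded in two levels: "The number of passes to reach final TICI 2b/3 will be categorized as 1 vs >1". The section asks for observed counts and percentages by arm, a model-based odds ratio, a Wald 95% CI and a p-value. If a patient had more than one thrombectomy, only the initial procedure counts.

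Two other places matter. SAP 4.6.2.4 makes angiographic reperfusion, "defined as achieving TICI 2b or TICI 3 at completion of the angiographic procedure", a secondary endpoint in endovascular patients, and it is fourth in the testing order of SAP Table 3. The one-pass endpoint is exploratory and does not appear in that order.

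**The concern.** A thrombectomy that ends below TICI 2b is neither one pass nor more than one pass under the SAP's coding. It drops out of the analysis instead of counting as a patient who did not succeed in one pass. Membership of the analysed group therefore depends on the procedure's result, which is known only after randomization and which the trial itself tests as a treatment effect. Randomization balances the arms as allocated; it does not balance the subsets that reached TICI 2b/3.

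SAP 4.6 says that exploratory endpoints, too, are evaluated for superiority, so the result will come with an odds ratio and p-value that invite a causal reading. At stake is the interpretation of one exploratory procedural endpoint: an odds ratio that differs from 1 could reflect who was removed from each arm and not how often one pass was enough.

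**Working it through.** The documents state no expected one-pass rate, failure rate or sample size for this endpoint, so there is no figure to reproduce. All rates below are assumptions, chosen to show how the rule behaves over a range.

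**Notation.** In one arm, let N be thrombectomies performed, S those ending in TICI 2b/3, and A those ending in TICI 2b/3 after one pass.

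- SAP rule: proportion A/S, odds A/(S − A).
- All performed: proportion A/N, odds A/(N − A).

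**Reference arm.** N = 100, S = 80, A = 40. The SAP rule gives 40/80 = 50.0%, odds 40/40 = 1.00. All performed gives 40/100 = 40%, odds 40/60 = 0.667.

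**Comparison arm, N = 100.** Odds ratios are comparison against reference, unadjusted.

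| Comparison arm | S | A | SAP rule | SAP OR | All performed | OR, all performed |
|---|---|---|---|---|---|---|
| 10 more failures, all would-be multi-pass | 70 | 40 | 40/70 = 57.1% | (40/30)/1.00 = 1.33 | 40% | 1.00 |
| 10 more failures, split evenly | 70 | 35 | 35/70 = 50.0% | (35/35)/1.00 = 1.00 | 35% | (35/65)/0.667 = 0.81 |
| 10 more failures, all would-be one-pass | 70 | 30 | 30/70 = 42.9% | (30/40)/1.00 = 0.75 | 30% | (30/70)/0.667 = 0.64 |
| 8 fewer failures, gained as multi-pass | 88 | 40 | 40/88 = 45.5% | (40/48)/1.00 = 0.83 | 40% | 1.00 |

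**Where the direction turns.** Suppose there are d extra failures and a share f of them would have been one-pass successes. The SAP proportion is (40 − f·d)/(80 − d). It equals 50% when 40 − f·d = 40 − 0.5·d, that is, when f = 0.5. Below that share the arm with more failures looks better under the SAP rule; above it, worse. The turning point is the reference arm's own one-pass proportion among successes.

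**A full reversal.** Arm A has 25 failures and 35 one-pass successes; arm B has 10 failures and 40 one-pass successes; N = 100 each. The SAP rule gives 35/75 = 46.7% against 40/90 = 44.4%, OR (35/40)/(40/50) = 1.09 in favour of A. Over all performed, 35% against 40%, OR (35/65)/(40/60) = 0.81 against A.

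**Effect of the size of the failure difference.** Hold A = 40 in both arms and let arm B have 10 failures (40/90 = 44.4%).

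- Arm A with 15 failures: 40/85 = 47.1%, OR (40/45)/(40/50) = 1.11.
- With 20 failures: 40/80 = 50.0%, OR (40/40)/(40/50) = 1.25.
- With 30 failures: 40/70 = 57.1%, OR (40/30)/(40/50) = 1.67.

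The artefact is small when failure rates are close and grows with the difference.

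**The case against.** The SAP definition answers a coherent question. The number of passes needed to reach TICI 2b/3 does not exist for a patient who never reaches it, and Protocol 6.4.3 leaves the details of exploratory analyses to the SAP, so narrowing the group there is not in itself a contradiction of the protocol. This stands as far as it goes. It justifies a description of passes among successes, but not a test between arms on a group selected by the procedure's result.

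Failures are also not hidden. SAP 4.6.2.4 reports TICI 2b/3 at completion by arm, so a reader would see an imbalance. This stands, with one limit: that endpoint covers endovascular patients without the clot-reached condition, so the two denominators may differ and the proportions may not recombine exactly.

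A reader might infer that more failures in an arm always raise its one-pass proportion. Nothing in the documents supports that. It depends on which patients fail, and the third row of the table shows the SAP rule pointing against the worse arm. The illustrations holding one-pass successes equal in both arms are the favourable case for the concern, not an expected result.

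Finally, restricting to performed thrombectomies is itself a post-randomization selection: SAP 4.6.3.3 and 4.6.3.7 describe planned procedures not performed after improvement or recanalization. This also stands. The all-performed odds ratios above remove the conditioning on success, but they are not free of all selection.

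**Conclusion.** The point holds as a minor one. SAP 4.6.3.5 conditions the comparison between arms on final TICI 2b/3. The resulting odds ratio can be distorted, and can reverse, when the arms differ in failures that come mainly from would-be multi-pass patients. For 10 extra failures per 100 thrombectomies, the SAP odds ratio runs from 1.33 to 0.75 depending on which patients fail, against 1.00 to 0.64 over all performed. These figures rest on assumed rates of 40 one-pass and 80 final successes per 100 in the reference arm.

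A reader might also take this as a threat to the trial's efficacy conclusion. It is not: the endpoint is exploratory, lies outside the testing hierarchy, and no confirmatory claim depends on it.

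**What to change.** In SAP 4.6.3.5:

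- Use all patients in whom thrombectomy was performed (clot reached) as the denominator.
- Define the event as exactly one pass in the initial procedure with final TICI 2b/3.
- Count all others as non-events, including those who never reach TICI 2b/3.
- Keep the number of passes among successes as a descriptive table without a p-value.
- State that the remaining restriction to performed thrombectomies is also post-randomization, and that the result should be read beside the endpoint in SAP 4.6.3.7 on planned thrombectomy not performed.

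The event should be built from the final TICI and pass count that the section already uses. Wording such as reaching the success grade after the first pass could require a TICI grade for each pass, and the documents do not show that one is recorded.

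The cost is a few sentences in the SAP, with no new data. The one-pass percentages become lower, because failures enter the denominator. If the SAP can no longer be amended, this version can be reported alongside the planned one and labelled as added.

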4.6.3.6 Quality of Life in Neurological Disorders

Quality of Life in Neurological Disorders (Neuro-QoL) is a set of self-reported measures that assesses the physical, mental, and social effects experienced by adults living with neurological conditions. In this study, the short forms (domains) collected are the adult versions of: Lower Extremity Function (Mobility), Depression, Ability to Participate in Social Roles and Activities, and Cognitive Function. Patients will be assessed using the Neuro-QoL at Day 90. Raw Neuro-QoL scores are normalized using data from the US general population with a T-score mean of 50 and standard deviation of 10. Tables for converting the raw scores are available in the Neuro-QoL user's manual for each short form (Neuro-QoL Scoring Manual, v2.0, 2015).

Missing values within a Neuro-QoL short form will be handled according to the rules described in the manual. First, confirm that 4 or 50% of items, whichever is greater, have been answered. If there a sufficient number of items is not missing, sum the response scores from the items that were answered. Multiply this sum by the total number of items in the short form. Finally, divide by the number of items that were answered. If fewer than 4 questions or 50% of the total number of questions are answered, then scores will be set to missing.

For each domain, Neuro-QoL scores will be summarized descriptively (mean, median, etc.). Linear models will be used to compare the mean score of the treatment group versus placebo, adjusting as specified in Section 4.6.

4.6.3.7 Planned Thrombectomy Not Performed

A planned thrombectomy may not be performed in some cases. This includes patients with partial or complete recanalization of the qualifying vessel occlusion who did not go to angiography suite because non-invasive imaging demonstrated recanalization, or patients who have undergone catheter angiography and are found to no longer to have an occlusion of the qualifying vessel.

The proportion of patients where a planned thrombectomy was not performed due to partial or complete recanalization will be summarized by treatment group and analyzed using logistic regression adjusted as specified in Section 4.6 but excluding the planned thrombectomy variable. Observed counts and percentages for tenecteplase and placebo arms, and model based odds ratio, corresponding Wald 95% CI and p-value will be produced.

4.6.3.8 Overall Survival at Day 90

Cumulative incidence of all deaths will be presented by means of Kaplan-Meier plots if there are sufficient events (at least 5 in each treatment group). Time to death since randomization will be analyzed with a stratified log-rank test using variables as specified in Section 4.6. Death occurred up to Day 90 visit (or within 120 days since randomization, which is the study day cut-off for efficacy outcome evaluation) will be included in the analysis. Patients who did not die up to Day 90 visit will be censored at the last study assessment date. In addition, death occurred after Day 90 visit and the relatedness of death is determined by having a related fatal AE will also be included in the analysis.

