24. Extensive early ischemic change (hypodensity) on non-contrast CT estimated to be >1/3 MCA territory, or significant hypodensity outside the $T_{max} > 6$ s perfusion lesion that invalidates mismatch criteria (if patient is enrolled based on CT perfusion criteria)
25. Significant mass effect
26. Acute symptomatic arterial occlusions in more than one vascular territory confirmed on CTA/MRA (e.g., bilateral MCA occlusions, or an MCA and a basilar artery occlusion)
27. Evidence of intracranial tumor (except small meningioma) acute intracranial hemorrhage, neoplasm, or arteriovenous malformation

End of Study

The end of this study is defined as the date when the last patient, last visit (LPLV) occurs or the date at which the last data point required for safety follow-up is received from the last patient, whichever occurs later. The end of the study is expected to occur 90 days (± 14 days) after randomization of the last patient in (LPI) the study.

Length of Study

The total length of the study, from screening of the first patient to LPLV, is expected to be approximately 3 years.

Investigational Medicinal Products

Test Product (Investigational Drug)

The investigational medicinal product (IMP) for this study is tenecteplase. The recommended total dose for this study is weight-based with 0.25 mg of tenecteplase per kg, not exceeding a

maximum dose of 25 mg. A single bolus dose should be administered over 5 seconds based on patient weight.

Comparator

Placebo is being used as the comparator since a thrombolytic is only FDA-approved in the United States for use out to 3 hours, and the standard of care guidelines support use out to 4.5 hours.

Statistical Methods

Primary Analysis

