5.6 ADVERSE EVENTS THAT OCCUR AFTER THE ADVERSE EVENT REPORTING PERIOD

The Sponsor should be notified if the investigator becomes aware of any serious adverse event that occurs after the end of the adverse event reporting period (defined as 90 *days* [± 14 days] after the dose of study drug), if the event is believed to be related to prior study drug treatment. These events should be reported through use of the Adverse Event eCRF. However, if the EDC system is not available, the investigator should report these events directly to the Sponsor or its designee, either by faxing or by scanning and emailing the paper Clinical Trial Serious Adverse Event/Adverse Event of Special Interest Reporting Form using the fax number or email address provided to investigators.

5.7 EXPEDITED REPORTING TO HEALTH AUTHORITIES, INVESTIGATORS, INSTITUTIONAL REVIEW BOARDS, AND ETHICS COMMITTEES

The Sponsor will promptly evaluate all serious adverse events and adverse events of special interest against cumulative product experience to identify and expeditiously communicate possible new safety findings to investigators, IRBs, ECs, and applicable health authorities based on applicable legislation.

To determine reporting requirements for single adverse event cases, the Sponsor will assess the expectedness of these events using the following reference document:

- Tenecteplase Investigator's Brochure

The Sponsor will compare the severity of each event and the cumulative event frequency reported for the study with the severity and frequency reported in the applicable reference document.

Reporting requirements will also be based on the investigator's assessment of causality and seriousness, with allowance for upgrading by the Sponsor as needed.

An iDMC will monitor the incidence of the above-listed anticipated events during the study. An aggregate report of any clinically relevant imbalances that do not favor the test product will be submitted to health authorities.

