AIS=acute ischemic stroke; CBC=complete blood count; CT=computed tomography; DWI=diffusion-weighted imaging; eCRF=electronic Case Report Form; FLAIR=fluid-attenuated inversion recovery; GOS=Glasgow Outcome Scale; GRE=gradient recalled echo; IV=intravenous; MRA=magnetic resonance angiography; MRI=magnetic resonance imaging; MRP=magnetic resonance perfusion; mRS=modified Rankin Scale; NIHSS=National Institutes of Health Stroke Scale; sICH=symptomatic intracranial hemorrhage; SOC=standard of care.

- ^a Patients should return to the clinic for follow-up 30 and 90 days after treatment. At Day 90, patients should have the study completion visit. If an in-person visit is infeasible, *only* the mRS should be performed by telephone. *All questionnaires can be collected by telemedicine except the Neuro-QoL.*
- ^b Medical history, including clinically significant diseases, surgeries, cancer history (including prior cancer therapies and procedures), reproductive status, smoking history, and use of alcohol and drugs of abuse, will be recorded at baseline. Demographic data will include age, sex, self-reported race/ethnicity, and veteran status.
- ^c Vital signs will include measurements of respiratory rate, pulse rate, and systolic and diastolic blood pressure, and temperature. Temperature will be required prior to randomization and will be performed with subsequent frequency per SOC. The frequency of respiratory rate, pulse rate, systolic and diastolic blood pressure measurements should reflect post-IV thrombolytic monitoring in AIS per SOC.
- ^d Patients should be weighed before randomization. Glucose (finger stick or blood draw) and coagulation tests (INR, aPTT, PT [only if the patient is taking an anticoagulant]) should be done. Results are required prior to randomization.
- ^e Platelet count results must be checked prior to randomization in patients with suspected coagulopathy. Electrolytes will also be collected. All other CBC and electrolyte results are NOT required prior to randomization.
- ^f All women of childbearing potential will have a urine/serum pregnancy test at screening. If a urine pregnancy test is positive, it must be confirmed by a serum pregnancy test.
- ^g A pre-stroke mRS will be estimated a baseline. Thirty and 90 days after treatment, patients should be evaluated using mRS preferably in the clinic; if an in-person visit is not feasible, the patient can be evaluated by telephone ([Appendix 2](#)).

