4.8.2.3 Mortality

Mortality rate up to study day 30 and day 90 will be summarized. These will be tabulated by primary cause of death. Deaths that occurred after the Day 90 visit date (up to 120 days since randomization) but captured in the database (e.g., as an outcome of an ongoing SAE) will not be included in the safety summaries unless the event is believed to be related with study treatment. All known deaths will be listed.

Details of any deaths will be presented in the form of individual patient listings.

4.8.2.4 Parenchymal Hematoma Type 2

The proportion of patients with PH2 intracranial hemorrhage within 72-96 hours follow-up visit will be summarized by treatment group.

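### SAP 4.6.3.8 censors survivors at the Day 90 visit but adds later deaths judged related, so the Kaplan-Meier tail after day 90 can be badly distorted

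*SAP*

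**What the plan says.** SAP 4.6.3.8 plans a Kaplan-Meier plot of the cumulative incidence of all deaths, provided each arm has at least 5, and a stratified log-rank test of time from randomization to death. Three sentences decide who counts and for how long.

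- Deaths included: "Death occurred up to Day 90 visit (or within 120 days since randomization, which is the study day cut-off for efficacy outcome evaluation").
- Censoring: "Patients who did not die up to Day 90 visit will be censored at the last study assessment date".
- Late deaths: "In addition, death occurred after Day 90 visit and the relatedness of death is determined by having a related fatal AE will also be included".

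For a patient who completes the study, the last assessment is the Day 90 visit. The schedule of activities (Protocol Appendix 1, footnote a) states: "At Day 90, patients should have the study completion visit". That visit is scheduled at 90 ± 14 days, so on days 76-104. SAP Table 2 accepts Day 90 clinical assessments on days 61-120. Section 4.6.3.8 sets no common cut-off day, no end to the plot, and no vital-status date that would keep survivors at risk after their visit.

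Two other rules bear on late deaths. Protocol 5.6 covers what reaches the sponsor once the reporting window has closed: the investigator is asked to pass on a serious event only "if the event is believed to be related to prior study drug treatment". SAP 4.8.2.3 deals with "Deaths that occurred after the Day 90 visit date (up to 120 days since randomization) but captured in the database" and keeps them out of the safety summaries unless they are believed related to treatment.

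**The concern.** Kaplan-Meier assumes that the patients still at risk at a given time represent those already censored. Here a survivor stops contributing at the Day 90 visit. A patient who completes the same visit and later dies of an event judged related contributes the extra time and then an event. The extra follow-up is granted because of the outcome, and only if a causality box is ticked.

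The step at each death is the current survival divided by the number still at risk, and that number falls quickly as Day 90 visits are completed. One late death can therefore move the curve by far more than its share of the arm. A mortality curve for a thrombolytic will be read as safety information, and the jump would appear in whichever arm has the late related death. Such a death also lies outside an endpoint named survival at Day 90.

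**Working it through.** **Inputs from the documents.** 228 patients per arm, 5% dropout, and assumed mRS 6 (death) of 12% on tenecteplase and 18% on placebo (SAP 2.3, Table 1). Visit windows are as quoted above.

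**The plan's own figure.** Section 4.6.3.8 gives no number. The sample-size statement that supplies the arm size and death rates does reproduce: a Wilcoxon-Mann-Whitney approximation with 216 evaluable per arm at two-sided 0.049 gives power 0.902, against the stated 90% or more. With 228 patients and 12% mortality, the chance of at least 5 deaths exceeds 0.999, so the plot would be drawn.

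**Assumptions of this check.** Dropouts leave at day 5 or day 30. All other deaths precede the visit window. Three visit spreads are tried, because the documents give windows but no distribution: uniform on days 76-104; clustered at day 90 with SD 5, kept within 76-104; and uniform on days 61-120.

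**One tenecteplase arm.** Deaths: 228 × 0.12 ≈ 27. Dropouts: 228 × 0.05 ≈ 11. Survivors: 228 − 27 − 11 = 190. Survival before any late death is about 87.8%. One of the 190 completes the visit and then dies of a related event on day t; the other 189 are censored at their visits.

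Drop at t = S(t−) / number at risk at t.

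Example, uniform on days 76-104, death on day 100: at risk ≈ 1 + 189 × 5/29 ≈ 33.6, and 87.8 / 33.6 ≈ 2.6 points. The simulated mean is 2.7, because the average of a ratio slightly exceeds the ratio of averages.

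Mean simulated results (number at risk; drop in points):

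| Day of late death | Uniform 76-104 | SD 5 around day 90 | Uniform 61-120 |
|---|---|---|---|
| 91 | 92; 1.0 | 88; 1.0 | 96; 0.9 |
| 95 | 67; 1.3 | 36; 2.5 | 83; 1.1 |
| 100 | 33.5; 2.7 | 6.5; 16 | 67; 1.3 |
| 102 | 20; 4.6 | 3.2; 35 | 61.5; 1.4 |
| 104 | 7.5; 14 | 1.7; 62 | 55; 1.6 |
| 110 | 1; 88 (to 0%) | 1; 88 (to 0%) | 36; 2.5 |
| 121 | 1; 88 (to 0%) | 1; 88 (to 0%) | 1; 88 (to 0%) |

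The placebo arm shows the same pattern, with a fall of about 82 points to 0% when the risk set is one.

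**Reference.** One death in 228 weighs 1/228 = 0.44 points. Had all 190 survivors stayed under observation, the step would be 87.8/190 = 0.46 points.

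**Log-rank.** With 27 v 41 deaths and roughly equal risk sets, and ignoring strata, Z ≈ (−14/2)/√(68/4) = −7/√17 = −1.70. One more tenecteplase death with equal numbers at risk adds 0.5 to observed minus expected and 0.25 to the variance: −6.5/√17.25 = −1.57. If the patient who dies is alone at risk, both contributions are zero.

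**The curve to day 90.** The Kaplan-Meier estimate at day 90 uses only events up to day 90. A death after day 90 cannot change it.

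**The case against.** The strongest reply is that little of consequence moves. The endpoint is exploratory and outside the testing hierarchy. Every distorted step in the table lies after day 90, so survival read at day 90 is unchanged. The log-rank statistic shifts by no more than one ordinary death would shift it. Mortality is also tabulated in SAP 4.8.2.3, and deaths enter the primary endpoint as mRS 6. The trigger is a fatal event judged related to a single bolus, with death after a completed Day 90 visit; the documents give no basis for estimating how often that would happen. All of this stands, and it confines the point to the tail of the plot.

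A second reply is that the 120-day parenthesis already sets a horizon. It can be read as admitting every death to day 120. On that reading the causality selection disappears up to day 120, but survivors are still censored at their last assessment, so follow-up after the visit is still granted only to those who die.

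A reader might infer three stronger things that the documents do not support.

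- That nobody else is at risk after the visit. Visits are spread over weeks; with the 76-104 window, 6.5 to 33.5 patients remain at risk on day 100 under the assumptions above.
- That Protocol 5.6 proves only related deaths are captured after the visit. It applies after the reporting period, which runs to 90 ± 14 days after dosing. Within that period Protocol 5.3.5.8 requires all deaths to be reported regardless of relationship. For deaths around days 91-104 the selection comes from the SAP's rule, not from ascertainment.
- That bleeding deaths would be the ones added. Nothing in either document shows which late deaths would be judged related.

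**Conclusion.** The rule is wrong as written, with limited reach. Extra follow-up is conditioned on death and relatedness, so the part of the Kaplan-Meier plot after day 90 does not estimate mortality in either arm. If one late related death occurs, the step is about 1 to 3 points soon after day 90. At day 100 it is about 3 points (visits uniform on days 76-104) to 16 points (SD 5), or 1.3 points if visits really spread over days 61-120. The curve falls to 0% survival, shown as 100% cumulative incidence, if the death comes after the arm's last visit: from day 105 if the protocol window is kept, or after day 120 if visits run to the end of the SAP window. The proper weight is 0.44 points. These sizes rest on the assumed visit spread and on SAP Table 1 mortality.

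It would be wrong to conclude that the survival estimate at day 90, the log-rank comparison or the primary analysis is compromised. They are not materially affected.

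**What to change.** In SAP 4.6.3.8:

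- Delete the sentence that adds related deaths after the Day 90 visit.
- Replace the inclusion rule, including the 120-day parenthesis, with: all deaths on or before study day 90 count, regardless of causality.
- Censor everyone else at the earlier of day 90 and the last date known alive, using the last study assessment date where no later contact is recorded.
- End the plot at day 90.

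Keep later deaths in the listing of all known deaths, and leave the safety summary rule in SAP 4.8.2.3 unchanged, so no late death is hidden.

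The cost is a few sentences in one section and no new data collection. There are two downsides. The few deaths after day 90 leave this curve, including some scored mRS 6 in the primary analysis because they precede a visit scheduled later in the window. A small asymmetry also remains before day 90: a patient seen early who then dies by day 90 counts, while a survivor seen early with no later contact is censored at that visit. With the tenecteplase-arm inputs and the three visit spreads used above, such a death on day 89 finds about 102 to 118 at risk and costs 87.8/118 to 87.8/102, or roughly 0.7 to 0.9 points. That stays under about 1 point per death.
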